Physical Activity and Pacemaker Study NCT03052829 Initial Protocol approved: 12/21/2016 Phy

Overview of approach: Based upon our previous work, the overall experimental design of this study is a small pragmatic randomized controlled trial (RCT). A general study diagram of events and procedures is present in Figure 2. Potential subjects who fit inclusion/exclusion criteria will be approached for enrollment once they are identified as candidates for permanent pacemaker implantation or as patients with already implanted Medtronic Revo or EnRhythm pacemakers. Individuals with, on average, less than 2 hours/day of active minutes over the prior 3 months (based in the pacemaker's internal accelerometer daily active minute reading) will be eligible for randomization. For individuals enrolled at the time of pacemaker implantation, the average active minutes for the time period of 3-6 months following implantation will be used to assess eligibility for randomization. At the time of enrollment all subjects will have a detailed medical history obtained. Thirty participants will be randomized across 2 parallel groups: an intervention group (n=15), or a Patient Usual Care (PUC) group (n=15). The PAC intervention follows the 5 A's (Assess, Advise, Agree, Assist, Arrange) model, which has been shown to be an effective clinical counseling tool for other health behaviors.14 Implanted Medtronic Pacemaker accelerometer data will be used to Assess physical activity levels. Subjects in the low active group will be referred to an intervention expert on the study staff. Eligible patients will then be Advised of their activity levels, and migrate through the 5 A's intervention model for 12 weeks. A fuller description of the intervention is included below. At the end of the 12 week active intervention, subjects in the intervention arm will enter a maintenance phase for an additional 3 months. During the study, pacemakers will be interrogated remotely or at clinic visits every 3 months. All subjects in the intervention arm will be contacted every 2 weeks to assess how they are doing with respect to the intervention. The study schema is shown in Figure 1, described in accordance with the CONSORT statement's recommendations for randomized clinical trials. An outline of study procedures is presented in Table 1.

Study setting.

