Subjects will be recruited from individuals who require permanent pacemaker placement at Froedtert Hospital and Zablocki VA Medical Center, both located in Milwaukee, WI.

Participant eligibility and recruitment.

Criteria for Enrollment and Randomization.

Inclusion Criteria:

1) Age \geq 55 years old

2) Clinical indication for placement of permanent pacemaker or currently implanted pacemaker

3) LVEF of \geq 50% by most recent echocardiogram.

4) Able to ambulate

5) Average active time of ≤ 2 hours/day based on Revo or EnRhythm Accelerometer read out for the 3 month period prior to enrollment

6) Able to take 650 steps over 10 minutes following pacemaker implantation (~2-2.5 mph walking speed)

Exclusion Criteria:

1) Follow up for implantation planned at a non-study center at the time of implantation.

2) Individuals with and expected life span of 1 year or less at the time of implantation

3) Known history of cognitive impairment or inability to follow study procedures

4) Lack of stable internet access

Randomization. Randomization will occur at the patient level. Upon potential eligibility being identified, subjects will be randomized in 3 blocks of 10 participants and randomized 1:1 to each study arm. We will enroll until we reach 15 subjects in each study arm who complete all study procedures. Randomization will be delivered via a random number generation sequence. Due to the nature of the trial, research staff, clinicians, and patients will not be blinded to patient assignment.

Physical Activity Counseling Intervention Group: The 12 week intervention is a multifaceted intervention that follows the 5 A's (Assess, Advise, Agree, Assist, Arrange) model, designed to be both simple to implement and follow for patients. It mimics a referral for education model that is used for patients who require a nutritionist or other specialist for behavioral modification. The intervention includes the following elements.

1) Assess: Subjects will undergo a physical activity assessment, utilizing the implanted Medtronic Pacemaker accelerometer data.

2) Advise: Eligible patients will be shown the graph from our recent publication demonstrating the relationship between decreased active minute time and mortality to help build the case that an intervention is necessary.

3) Agree: Those patients who agree enter into a shared decision making process to behavior change – in this case modifying physical activity behavior in an effort to decrease sedentary time.

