4) Assist: The patient will receive a written prescription that includes their baseline Medtronic Pacemaker accelerometer data, and a target to increase their activity. Activity will be increased using the following:

a. Self-regulatory monitoring: A pedometer with a target to increase steps by 10% per week, to a target of 10,000 steps/day. A calendar will be given for patients to write down daily amounts.

b. Brief printed support materials – on different behavioral strategies to increase active behaviors

c. A list of freely available internet-resources

d. Bi-weekly telephone support: A member of the study staff will call each participant randomized to the PAC intervention group every other week. Calls will be limited to 5 minutes and used to offer support, advice, and solicit feedback.

5) Arrange: A follow-up visit will be arranged for week 12, to retrieve outcome data for physical activity from the implanted Medtronic Pacemaker accelerometer. Alternatively, data will be obtained through convenient methods.

Overall, our approach employs key strategies proven to increase the adoption and retention of lifestyle integrated habitual physical activity in older adults.15,16 These strategies included the use of frequent feedback,15 selfregulation of activity,17,18 education and practice in realistic behavioral change strategies and goal setting,16 and rewarding.19

Patient Usual Care (PAC) Group: The PAC group will undergo Implanted Medtronic Pacemaker Accelerometer data retrieval, but this data will not be shown to the patient, nor used to alter behavior. This group will follow their typical clinical routine, and therefore represent a usual care approach.

Communication of Physical Activity information: All individuals with pacemakers will undergo interrogation of their device every 3 months during entire study period, including intervention phase and follow-up phase.

Outcomes: The primary outcome for this study is the number of active minutes as measured by the Medtronics Implanted Pacemaker accelerometer.

Statistical Methods: Baseline demographic and clinical data will be compared between groups by unpaired t-tests, Chi-squared tests, or non-parametric equivalents as appropriate. The primary outcome will be compared between

Data Analyses

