SPSS 24 and SigmaStat 12.5 were employed for data analyses. Data will be analyzed on a per protocol basis given that the goal of this pilot. Baseline characteristics will be compared between groups using unpaired t-tests, chi-

square, or Fisher's Exact test as. Differences in step counts and pedometer determine active time over the study period will be investigated using general linear models for repeated measures with the randomization group assignment as the between subjects variable and a three factor within subjects comparisons representing the three measurement time points with the Tukey test applied for post-hoc comparisons if significance of the overall models was detected. Correlations between step count measurements and PDAH measurements were performed using Pearson's r test. *P* < 0.05 were considered significant.

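### The readable between-arm model names pedometer active time where the declared outcome is pacemaker active minutes, and its gate to Tukey comparisons does not isolate an arm effect

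*Combined protocol and SAP*

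**What the plan says.** The Outcomes paragraph of the combined protocol and SAP names one primary outcome: "The primary outcome for this study is the number of active minutes as measured by the Medtronics Implanted Pacemaker accelerometer". The device is also the source of activity time elsewhere. The Overview of approach screens on the pacemaker's "internal accelerometer daily active minute reading", and inclusion criterion 5 takes average active time "based on Revo or EnRhythm Accelerometer read out for the 3 month period prior to enrollment". Under Arrange, the outcome visit is also tied to the device: "A follow-up visit will be arranged for week 12, to retrieve outcome data for physical activity from the implanted Medtronic Pacemaker accelerometer".

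Under Data Analyses, the model sentence reads: "Differences in step counts and pedometer determine active time over the study period will be investigated using general linear models for repeated measures". Randomised group is the between-subjects variable and time is the within-subjects variable, "representing the three measurement time points with the Tukey test applied for post-hoc comparisons if significance of the overall models was detected". The significance level is 0.05. A later sentence correlates step counts with PDAH, an abbreviation not defined in the readable text.

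Under Statistical Methods, the sentence that would describe the primary comparison stops at "The primary outcome will be compared between".

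**The concern.** There are two separate problems in the Data Analyses model.

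**Dependent variable.** Taken literally, the model analyses a different instrument from the declared outcome. The readable text describes the pedometer only as a step-counting, self-monitoring aid in the counselling arm (item 4a). The usual-care paragraph mentions device data retrieval and no pedometer. A literal reading therefore gives the model a variable with no described source in the control arm.

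**Gate.** A model with two groups and three time points has a group term, a time term and a group-by-time term. The condition for going on to Tukey comparisons does not say which of them counts. A time effect common to both arms says nothing about counselling, yet it could satisfy the condition. If baseline is one of the three time points, the group term averages in a pre-treatment value and so dilutes a difference that arises afterwards. This second problem remains even if the first is only a wrong word.

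At stake is whether a reader of the results can tell which measure was tested, and whether a significant model reflects a difference between arms.

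**Working it through.** **Textual check.** Active time or active minutes is attributed to the pacemaker in the Overview of approach, inclusion criterion 5, Arrange and Outcomes. Only the Data Analyses sentence attributes it to a pedometer. That sentence also lists step counts separately, which fits pedometer steps plus device time. A slip for pacemaker is the likeliest reading, but the sentence as written does not match the declared outcome.

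**Numerical illustration.** The plan gives no power, effect size, SD or correlation, so it has no figure to reproduce.

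- From the documents: 15 per arm, two arms, three time points, level 0.05.
- Assumed: SD 1, equal correlation r between any two time points, two-sided tests, first time point at baseline and two follow-ups after it, and the effect sizes below.

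*Time term, no arm difference.* Both arms move by 0.5 SD at both follow-ups, so the means are 0, 0.5, 0.5. The deviations from their average (1/3) are −1/3, 1/6, 1/6, and the squares sum to 1/6. Noncentrality = 30 × (1/6) / (1 − r). At r = 0.5 this is 10. With F on 2 and 56 df (critical value 3.16), the term is significant in 79.3% of trials.

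*Group term, 1 SD arm effect at both follow-ups.* The differences are 0, 1, 1, with average 2/3. SE = √[2 × ((1 + 2r)/3) / 15]. At r = 0.5, SE = 0.298 and the ratio is 0.667/0.298 = 2.24. With t on 28 df (critical value 2.05), power is 57.9%.

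*Group-by-time term, same effect.* The squared deviations of 0, 1, 1 sum to 2/3. Noncentrality = (15/2) × (2/3) / (1 − r) = 10 at r = 0.5. Power is 79.3%.

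*Difference in change from baseline to the first follow-up, same effect.* SE = √[4(1 − r)/15] = 0.365 at r = 0.5, ratio 2.74, power 75.3%.

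| Quantity | r = 0.3 | r = 0.5 | r = 0.8 |
|---|---|---|---|
| Time term, both arms +0.3 SD | 26.8% | 36.1% | 74.7% |
| Time term, both arms +0.5 SD | 64.0% | 79.3% | 99.5% |
| Group term, 1 SD sustained | 67.5% | 57.9% | 47.4% |
| Group-by-time, 1 SD sustained | 64.0% | 79.3% | 99.5% |
| Change to first follow-up, 1 SD | 60.8% | 75.3% | 98.7% |
| Group term, 1 SD gone by second follow-up | 22.7% | 19.1% | 15.7% |
| Group-by-time, 1 SD gone by second follow-up | 64.0% | 79.3% | 99.5% |

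The fading pattern is included because, after 12 weeks, "subjects in the intervention arm will enter a maintenance phase for an additional 3 months". The documents do not predict that the effect fades.

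*No effects of any kind.* Treating the three tests as independent, the chance that at least one is significant is 1 − 0.95³ = 14.3%. Simulation of 40,000 trials per setting gave 14.0% to 14.5%, against 5% for one named term.

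**The case against.** **The wrong word may be only that.** The textual evidence favours a slip, and then the harm of the literal reading does not arise. This stands, and it reduces the first problem to a correction that the sponsor should confirm.

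**Text is missing.** The Statistical Methods sentence may have named the primary test. Table 1 and the figures cited in the Overview are not in the readable text. They may name the time points, show whether steps are collected in both arms, or clarify PDAH. This also stands. A reader might infer that the trial has no primary analysis, or that the Data Analyses model alone decides its conclusion. The documents support neither inference. Unnamed time points and an undefined abbreviation are not counted as errors here.

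**The gate is not a success rule.** It only opens Tukey comparisons. A reader might take the 79% as a false-positive rate for counselling, and it is not one. In simulations with equal change in both arms and any significant term opening the gate, it opened in 34% to 99.5% of trials. A false same-time arm difference then followed in about 1% with Tukey over all six cells and pooled error, or 9% to 11% with pairs within each time and pooled error. With six cells and the within-subject error term the figure was 4% to 33%. The consequence depends on a Tukey implementation that the readable text does not specify.

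**It is a pilot, and group is in the model.** Both are true. A between-arm test can be derived from the model, but the model sentence does not designate one, although a 0.05 threshold is applied.

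**Conclusion.** The concern holds within limits. As written, the Data Analyses model names a different measure from the declared primary outcome, probably by a slip, and its gate can be opened by a time effect that both arms share. The dilution argument holds only if baseline is one of the three time points.

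The choice of term can matter. For a sustained 1 SD effect at correlation 0.5, power is about 58% on the group term and 79% on group-by-time. The gap widens at correlation 0.8. At correlation 0.3 it is small and slightly favours the group term (67.5% against 64.0%). All these figures rest on assumed effect sizes, correlations and time points. This is a wording correction that should be made, with medium confidence because of the missing text.

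**What to change.** Under Data Analyses:

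1. After the sponsor confirms the intended measure, name active minutes per day from the implanted pacemaker accelerometer as the primary dependent variable.
2. Replace the overall-model condition with the group-by-time term as the deciding between-arm test. Report with it the between-arm difference in change from baseline to week 12. Confirm that baseline is one of the three time points, since this choice relies on it.
3. Keep Tukey comparisons as supporting analyses.
4. Make the Statistical Methods sentence on the primary comparison agree.

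No new data are needed: devices are interrogated every 3 months in all participants. The cost is that the team commits to one test in advance. The group-by-time term alone does not show when the arms differ or in which direction, which is why the week 12 estimate should accompany it.

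### The repeated-measures model may share one error term across a capped baseline and uncapped follow-up readings, and drops randomized patients with a missing reading; a baseline-adjusted mixed model is a cheap improvement

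*Combined protocol and SAP*

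**What the plan says.** Under Data Analyses the plan states: "Differences in step counts and pedometer determine active time over the study period will be investigated using general linear models for repeated measures". The model is specified as "general linear models for repeated measures with the randomization group assignment as the between subjects variable", and time, at three unnamed points, is the within-subjects factor. If the overall model is significant, the analysis continues "with the Tukey test applied for post-hoc comparisons". The section names no covariance structure, sphericity check or correction, error term for the Tukey tests, or method for missing readings. It also says "Data will be analyzed on a per protocol basis given that the goal of this pilot".

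Three other places matter:

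- Inclusion Criteria, item 5, requires "Average active time of ≤ 2 hours/day based on Revo or EnRhythm Accelerometer read out". This caps the pacemaker reading at entry; nothing caps it later.
- Outcomes names pacemaker active minutes as the primary outcome. The sentence under Statistical Methods that would give its comparison breaks off, so the repeated-measures model is the only longitudinal method in the surviving text.
- Randomization says "We will enroll until we reach 15 subjects in each study arm who complete all study procedures".

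Readings at baseline, 3 and 6 months are inferred from the three-monthly interrogations, the 12-week intervention and the 3-month maintenance phase.

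**The concern.** A classical repeated-measures analysis with post-hoc tests usually takes one pooled error for all three readings. For a between-arm comparison at one visit, that is right only if the variance is the same at every visit. An upper limit on entry values compresses the baseline spread, and follow-up values are free to exceed it, particularly as the intervention aims to raise activity. If the capped variable is the one modelled, the pooled error averages in a small baseline variance and understates the uncertainty of the follow-up comparisons, which carry the visit-specific results.

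Two further costs come with this model. Baseline enters as one of three outcomes rather than as a covariate, so the comparison at a visit gains no precision from it. A patient without all three readings contributes nothing, even when one follow-up reading exists.

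**Working it through.** **Inputs from the documents.** 15 per arm (Overview of approach); significance at 0.05, sidedness not stated and taken as two-sided; three readings; cap of 120 min/day at entry. The plan gives no SD, correlation, effect size or dropout rate, so there is no power figure to reproduce and everything below rests on stated assumptions.

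**Step 1: size of the standard-error distortion.** Let v0 be the baseline variance and v the variance at each follow-up. Averaging over three readings gives (v0 + 2v)/3, so for a between-arm comparison at follow-up

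k = pooled SE / true SE = √[(v0/v + 2)/3].

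Assume baseline is normal(120, 60) truncated to 0-120, which has mean 77 and SD 30. The approximate type I error is 2[1 − Φ(1.96k)]. With two arms at one visit, Tukey equals the t comparison, so no multiplier applies. The simulations used 20,000 null trials per scenario, baseline/follow-up correlation about 0.6 and follow-up/follow-up correlation about 0.8.

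| Follow-up SD (assumed) | v0/v | k | Approx. type I | Simulated, ungated | Gated on group-by-time | Gated on group or group-by-time |
|---|---|---|---|---|---|---|
| 25 | 900/625 = 1.44 | 1.071 | 3.6% | 3.5-3.9% | – | – |
| 35 | 900/1225 = 0.735 | 0.955 | 6.1% | about 6% | 1.2% | 4.2% |
| 45 | 900/2025 = 0.444 | 0.903 | 7.7% | about 7.5% | 2.1% | 5.0% |
| 60 | 900/3600 = 0.25 | 0.866 | 9.0% | about 9% | 3.1% | 5.8% |

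If a time effect alone is allowed to open the gate, the error returns to about 6-8%. Using each visit's own variance gives about 5% throughout.

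**Step 2: a second set of assumptions.** Here 25-80% of patients are eligible, readings correlate 0.5-0.8, and 6,000 null trials are run per scenario.

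- Modelled variable is the capped pacemaker reading: v0/v is 0.30-0.80. The formula gives √(2.30/3) = 0.876 and √(2.80/3) = 0.966; the simulation gives 0.875-0.967. The SE is about 3-13% too small, and 95% intervals at follow-up cover 91.1-94.3%.
- Modelled variable is a pedometer measure correlated 0.4-0.7 with that reading: v0/v is 0.69-0.98, so k is √(2.69/3) = 0.947 to √(2.98/3) = 0.997. The SE is 0.3-5% too small, and coverage is 93.6-95.2%.
- A separate variance per visit covers 94.5-95.5% in every scenario.
- Uncorrected group-by-time test: type I error 4.3-5.9%, with sphericity epsilon 0.98-1.00. Under the Step 1 assumptions it is 5.4-6.2%.
- Between-arm differences in change from baseline: coverage 94.8-95.9%.

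**Step 3: use of baseline.** With correlation 0.6, adjusting for baseline leaves 1 − 0.6² = 0.64 of the variance. A 0.8 SD effect then counts as 0.8/√0.64 = 1.0 residual SD. In simulation the baseline-adjusted comparison at a visit held 5% error and had about 74% power for 0.8 SD, against about 53-65% for the pooled-error comparison. This concerns the visit-specific comparison, not the group-by-time test, which already uses baseline.

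**Step 4: missing readings.** At an assumed 5% or 10% missing per follow-up reading, 1 − 0.95² = 9.75% or 1 − 0.90² = 19% of patients miss at least one of two. Counting all three readings, it is 14% or 27%. Because enrolment continues to 30 completers, the number needed is 30/0.95² = 33.2 (34) to 30/0.95³ = 35.0 (35) at 5%, and 30/0.90² = 37.04 (38) to 30/0.90³ = 41.2 (42) at 10%. About 4-5 or 8-12 randomized patients would be set aside.

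**The case against.** The strongest reply is that the model, as written, is for step counts and pedometer active time, whereas the cap applies to the pacemaker reading. Taken literally, the truncation is indirect and its effect small (Step 2). This stands. The point has full force only if pedometer is a slip for pacemaker, or if the same method is used for the primary outcome, and the text settles neither.

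Second, the Tukey tests run only after a significant overall model, so ungated error rates overstate what the plan would do. This also stands, with one limit: the plan does not say which effect counts as the overall model, and a real rise over time in both arms could open the gate.

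Third, a reader might infer that the 3- and 6-month standard errors are simply wrong, or that treatment effects will be declared too often. The documents do not support that. They fix no error term, give no SDs, and leave open a follow-up SD below the baseline SD, which makes the comparison conservative. The group-by-time test stays close to 5%.

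Fourth, a reader might infer that incomplete patients shrink the analysis: about 3 or 6 of a fixed 30 (0.0975 × 30 = 2.9; 0.19 × 30 = 5.7), taking power for 0.8 SD from 56% to 52% or 47%. The completer rule in Randomization rules this out, because those patients are replaced. Nor does dropping patients by itself make a standard error wrong. The restriction also comes from the completer rule and the per-protocol set as much as from the model.

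Finally, this is a small study that calls itself a pilot, and a conventional repeated-measures model is common. That bears on the weight of the point, not on whether a better method is available at little cost.

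**Conclusion.** The point holds in a limited form, as a cheap improvement. The plan leaves the error structure and missing-data handling open, and the usual defaults fit this design poorly if the capped pacemaker reading is modelled. The likely distortion is then a modest understatement of follow-up standard errors, conditional on follow-up spread exceeding baseline spread; it is close to negligible for a pedometer measure. After gating, little excess type I error remains unless time alone opens the gate.

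The firmer reasons to change are the unused baseline information at each visit and the exclusion of randomized patients who have usable follow-up data, with possible selection. All sizes rest on assumed SDs, correlations, eligibility fractions and missing rates, with approximately normal data. No conclusion is drawn on 3 versus 6 months: the direction of any error there depends on the correlations assumed.

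**What to change.** State which variable the model analyses, pacemaker or pedometer, and whether it is the primary-outcome analysis. For the follow-up readings, replace the repeated-measures general linear model with a linear mixed model: arm, visit, arm-by-visit and baseline value as fixed effects, unstructured covariance between visits, and Kenward-Roger or Satterthwaite degrees of freedom. Include every randomized patient with at least one follow-up reading, and report the arm difference at each visit with its own standard error and interval in place of pooled-error Tukey tests.

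The per-protocol sentence has to be amended for this analysis, because changing the model alone would not bring back patients whom that set excludes. Patients with no follow-up reading still contribute nothing and should be counted by arm.

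The cost is SAP wording, a different software procedure and one or two extra covariance parameters. No new data are needed.

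### Randomization is in blocks of 10, but the repeated-measures model has no block term; if blocks differ, the between-subjects group test is conservative and loses precision

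*Combined protocol and SAP*

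**What the plan says.** The Randomization paragraph states that "subjects will be randomized in 3 blocks of 10 participants and randomized 1:1 to each study arm", with allocation made as patients are found eligible. Three blocks of 10 at 1:1 give 5 + 5 per block and 15 + 15 overall, which matches the planned 30. Non-completers are replaced: "We will enroll until we reach 15 subjects in each study arm who complete all study procedures".

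Data Analyses describes the model: "Differences in step counts and pedometer determine active time over the study period will be investigated using general linear models for repeated measures". It is fitted "with the randomization group assignment as the between subjects variable" and with "a three factor within subjects comparisons representing the three measurement time points". Block, site, season and calendar date are not named in the analysis. The decision rule is P < 0.05, and no confidence intervals are planned. The analysis is per protocol.

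The Outcomes paragraph says: "The primary outcome for this study is the number of active minutes as measured by the Medtronics Implanted Pacemaker accelerometer". In the available text the sentence on how that outcome will be compared breaks off, so its model cannot be read.

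**The concern.** Blocking with 5 + 5 per block removes any difference in level between blocks from the comparison of arms. The analysis benefits from this only if block is in the model. Otherwise the variation is pooled into the residual, the standard error overstates the true sampling variability of the arm difference, and the test rejects less often than its nominal 5%.

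Blocks could plausibly differ. If they fill in order of accrual, they follow calendar time. The Overview also brings in two kinds of patient on different timetables: those with existing implants are judged on their prior 3 months, and new implants on activity 3 to 6 months after implantation. Both are reasons to expect possible differences, not evidence of them. At stake is precision and power in a trial of 30 patients.

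**Working it through.** **Inputs from the documents.** N = 30; 3 blocks of 10; 5 + 5 per block; group as the only named between-subjects variable; significance level 0.05.

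**Assumptions.** Two-sided testing (sidedness is not stated). The between-block share of outcome variance, rho, is not in the documents and is varied from 0 to 20%. Total variance is set to 1. The calculation treats one value per patient, so it applies to the between-subjects group comparison and not to group-by-time. Blocks are taken as complete.

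**The plan's own figure.** 3 x 10 = 30 = 15 + 15, which agrees. No effect size, SD or power is given, so no power calculation can be reproduced.

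**Step 1: error variance.** With block in the model, the residual has 30 - 4 = 26 degrees of freedom and expected mean square 1 - rho. Without block, it has 28 degrees of freedom. The 2 block degrees of freedom, each with expected mean square (1 - rho) + 10 rho, are pooled in:

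[26(1 - rho) + 2((1 - rho) + 10 rho)] / 28 = (1 - rho) + (20/28) rho.

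The true variance of the arm difference is (1 - rho) x 2/15 in both cases, because block effects cancel at 5 + 5.

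**Step 2: interval width.** Width without block / width with block = (t28/t26) x sqrt(1 + (20/28) x rho/(1 - rho)), where t28 = 2.0484, t26 = 2.0555 and t28/t26 = 0.9965. The effect of adding block is the reciprocal minus 1.

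- rho 0: 1/0.9965 gives +0.3%
- rho 0.05: 1/1.0151 gives -1.5%
- rho 0.10: 1/1.0353 gives -3.4%
- rho 0.20: 1/1.0819 gives -7.6%

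**Step 3: break-even.** Set the ratio to 1. Then rho/(1 - rho) = ((t26/t28)^2 - 1) / (20/28) = 0.00697/0.7143 = 0.00975, so rho = 0.0097, or about 1%.

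**Step 4: simulation.** 40,000 trials per setting, normal outcome; power is for an assumed difference of 1 SD.

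| rho | Width change on adding block | Type I error, without / with block | Power, without / with block |
|---|---|---|---|
| 0 | +0.2% | 5.0% / 5.0% | 75.5% / 75.2% |
| 0.05 | -1.5% | 4.6% / 5.0% | 76.1% / 77.0% |
| 0.10 | -3.4% | 4.3% / 5.0% | 77.6% / 79.6% |
| 0.20 | -7.4% | 3.6% / 5.0% | 79.6% / 83.9% |

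The simulation agrees with the formula to within about 0.2 percentage points.

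**Step 5: the group-by-time test.** This test uses differences between a patient's own measurements. A block effect that is constant over time drops out of those differences, so leaving it out costs nothing there. Only a block effect that changes over the three time points stays in the within-subjects error, and only a block-by-time term removes it. The documents give nothing from which to size that component.

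**The case against.** The strongest case against is that the test as planned is valid. Leaving block out brings no bias and no excess of false positives, and in a 30-patient pilot it is reasonable not to spend degrees of freedom on a factor of unknown importance. Several parts of this case stand.

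- The figures describe a single value per patient. The planned model has three time points, and differing change between arms is tested by group-by-time, from which stable block differences already cancel. The figures therefore apply only to the between-subjects comparison.
- Nothing in the documents supports a particular rho. At 5% the gain is only 1.5%.
- Block is a rough proxy for season. No accrual period is given, so a block could span several seasons or all three could fall within one. Each patient is also followed through 12 weeks of intervention and 3 months of maintenance, so a patient's own measurements can cross seasons. That the hospitals are "both located in Milwaukee, WI" shows location, not a seasonal effect on this outcome.
- The visible model covers step counts and pedometer active time. The text does not show whether the primary analysis omits block.
- Replacing non-completers and analysing per protocol can leave more than three blocks, or blocks that are not 5 + 5, so the balanced figures are approximate.

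A reader might also infer that recruitment route (new or existing implant) needs its own term. The documents do not support that. They give no route mix and no route effect on the outcome, and chance imbalance on a factor that was not stratified is not an error of analysis.

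What the objection does not remove is that block is part of the design, so including it is justified whatever makes blocks differ. The trade is also lopsided: about 0.3% in width if blocks are identical, against 3.4% at an assumed share of 10%.

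**Conclusion.** The point holds as a conditional matter of efficiency. Randomization is blocked, the stated model has group as its only between-subjects variable, and any stable between-block variation is therefore counted as error in the between-subjects group comparison. If such variation exceeds about 1% of the total, leaving block out loses precision: about 1.5% in interval width at an assumed 5%, 3.4% at 10% and 7.5% at 20%, with type I error falling to 4.6, 4.3 and 3.6%. Because the plan names only a P-value rule, the practical effect is on P values and power.

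A reader might infer that the plan's intervals are in fact widened by calendar or seasonal variation. The documents do not support that: they give no between-block variance, no accrual dates and no planned intervals, and below the break-even share the model without block is marginally narrower. Nor do they support a reading that the omission biases the treatment effect or inflates false positives; if blocks differ, the error runs in the conservative direction.

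These results rest on complete 5 + 5 blocks, two-sided testing at 0.05 and one value per patient.

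**What to change.** Prespecify randomization block as a between-subjects factor in the Data Analyses model, together with block-by-time and without group-by-block. State that the same terms apply to whichever model is used for accelerometer active minutes. Use the blocks actually generated: if replacing non-completers creates more than three, include them all and do not force three levels.

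The cost is a line in the analysis plan. With three blocks, the between-subjects error goes from 28 to 26 degrees of freedom, and intervals for that comparison are about 0.3% wider if blocks do not differ. Block-by-time takes the within-subjects error from 28 x 2 = 56 to 26 x 2 = 52 degrees of freedom. Each further block costs one more between-subjects and two more within-subjects degrees of freedom. No change to randomization or data collection is needed, provided the block number is kept with each patient's record.
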